***Traditional Intravenous Fluid versus Oral Fluid Administration in Primary
Total Knee Arthroplasty: A Randomized Trial***

Version 8.0 July 6th, 2017 - NCT03719378

Traditional Intravenous Fluid versus Oral Fluid Administration in Primary Total Knee Arthroplasty: A Randomized Trial

1. Purpose: Evidence-based guidelines on optimal perioperative fluid management have not been established in patients undergoing orthopaedic surgery. Typical intraoperative and post-operative fluid management has been arbitrary without evidence based guidelines established following total joint replacement. We have observed many patients post-operatively with side effects such as fluid overload leading to medical complications requiring either prolonged hospitalization or readmission. Additionally, this overload may lead to wound healing complications secondary to fluid shifts which may be devastating in this patient population. Recent randomized trials in major abdominal surgery suggest that large amounts of IV fluid may increase morbidity and hospital stay. Additionally, this increase fluid may be detrimental in patients with anastomosis leading to failure and/or complications in this patient population. We have defined to specific groups of interest to study in this patient population with regards to fluid management. The first group is the “traditional” IV fluid group where the anesthesiologist gives an unspecific amount of fluid intraoperatively and post-operatively the patient gets a set amount of fluid based on “protocol” on the orthopaedic floor (i.e. 75 cc/hour until good oral intake). This is the protocol utilized by most orthopaedic practices throughout the United States. The second group is defined as patients who are given a specific protocol preoperatively to optimize hydration, followed by limited fluids intraoperatively based on physiologic parameters. This study will investigate the effects of two regimens of intraoperative fluid management (“traditional” vs. “oral”) with physiologic and patient function as primary outcome measures after surgery.

2. Procedures:

- Patients meeting the inclusion criteria who are schedule for unilateral primary TKA will be identified.
- The patients will be approached regarding the study (in clinic by research staff) and if the patient is agreeable, informed consent will be obtained.
- The patients will be randomized into the traditional vs. oral treatment groups (see below for details and protocol). The protocol for each group will be placed in sealed envelopes, 65 for each group, and picked randomly for each patient.
- The patients will attend their normal preoperative visits with the surgical team as well as their regularly scheduled preoperative clearance visit with the medical doctor (Surgery Welcome Center)
- Standard preoperative labs will be obtained (hematocrit, basic metabolic panel), at their preoperative appointment
- Additional preoperative labs will include urine specific gravity to monitor patient hydration which will be obtained the morning of surgery; this will be paid for by the CJR research fund.
- Standard laboratory values (hematocrit and basic metabolic panel) will be obtained postoperative day #1 and #2, if the patient has not been discharged.
- Urine output will be monitored on postoperative day #1 and #2 which is standard protocol
- Additional test will include urine specific gravity on postoperative day #1 and #2 as a marker of hydration as long as the patient is still in the hospital. If the patient is discharged postoperative day #1 we will collect this once in the morning, and once more before they are discharged. Payment of the cost of these laboratory evaluations will come from CJR research funds.
- Patients are encouraged to attend physical therapy 2-3 times a week for 6 weeks. Physical therapy log is attached with ROM and Girth measurement collected once a week for 4 weeks.
- Hematocrit, basic metabolic panel and urine specific gravity 2 weeks postoperatively at their routine follow-up visit will also be obtained. The cost of these laboratory tests will come from CJR research funding.
- Sixty-five patients in each group will be recruited for this study (see stats for power analysis). We will increase our number of enrollment to 75 in each group to account for patients that drop out and withdrawals from the study.

Traditional Fluid Protocol

- NPO Clears and Food after midnight.
- 2 Liters of lactated ringers administered by anesthesia intraoperatively.
- Postoperatively - 2 Liters of Crystalloid while in PACU and Inpatient Room for a Total of 4 Liters of Crystalloid within 24 hours.
 - Patient will receive 500 milliliters while in PACU and 1500 milliliters while in their Inpatient Room, for a total of 2 Liters.
- Spinal drug choice standardized: 9 mg (1.2 ml) –11.25 mg (1.5ml) of Spinal Bupivacaine 0.75%with Dextrose 8.25%. We have also attached the spinal anesthesia guidelines that will be followed for this study (see attached).
- Ondansetron 4mg IV given prior to regional anesthesia; repeat x 1 prior to the end of surgery.
- Ultrasound Guided Adductor Canal Block using 30 ml of Ropivacaine 0.35% Preservative Free.
- Normal diet postoperatively.

Oral Fluid Protocol

- Patients encouraged to drink a minimum of three, 20 ounce cups of clear liquid per day each day for the 3 days prior to procedure. Examples of clear liquids include water, clear sports drinks, fruit juices without pulp. Please limit caffeinated and carbonated beverages to no more than 1 drink per day.
- NPO Food/Milk: none beginning 8 hours prior to procedure time.
- NPO Clear Liquids — Patients are asked to drink 10 ounces of clear liquid 4 hours prior to their scheduled procedure time.
- In the preoperative holding area, an IV is started in the patient; and the patient is given Lactated Ringers IV fluid at a rate of 75ml/hr. The IV fluids will be stopped and the IV hep-locked in the PACU when the patient is taking PO fluid; the total amount of IV fluids given to the patient is charted and is not to exceed 500ml total.
- Spinal drug choice standardized: 9mg (1.2 ml) -11.25(1.5ml) mg of Spinal Bupivacaine 0.75%with Dextrose 8.25%.
- Ondansetron 4mg IV given prior to regional anesthesia; repeat x 1 prior to the end of surgery
- Ultrasound Guided Adductor Canal Block using 30 ml of Ropivacaine 0.35% Preservative Free. Normal diet postoperatively.
- PO fluid protocol implemented on the floor immediately postop: a minimum of three, 20 ounces cups of liquid per day for 3 days. Patients can drink more than the minimum if they feel dehydrated.

Primary Outcomes

A. Body Weight – scales will be purchased and provided to the patient while participating in the study. All weights will be obtained on the same scale for each patient to assure consistency of measurements. Measurements will be performed in the preoperative holding area prior to surgery, the evening of surgery on the orthopaedic floor and every morning the patient is hospitalized using the same scale assigned to that patient. Body weight measurements will be repeated at home 48 hours' post-discharge and at one and two weeks either at home or in the clinic with the same scale as previously utilized. An additional measurement will be obtained at 3 weeks postoperatively if the patient's body weight at 2 weeks has changed more than +/- 2% from their preoperative value. Funding of the cost of the scales will come out of the CJR research funding.

B. Knee Range of Motion: This will be assessed preoperatively (at their clinic appointment), on POD #1 and 2 by the research staff if the patient has not been discharged, and at 1, 2, 3 and 4 weeks postoperatively by the outpatient physical therapy office. Patient standardized forms will be provided to the outpatient physical therapists to record all post-hospital measurements. Measurements will be done with a standard goniometer.

C. Leg Anthropometric (Girth) Measurements: girth measurements will be performed at 5 & 10 cm suprapatellar, midpatella, and 10 cm infrapatellar with the use of a standard tape measure. These measurements will be collected at their pre-operative visit by research staff, POD 1 and 2 by research staff, if the patient has not been discharged and post-discharge measurements will be performed by the outpatient physical therapist at the same intervals and recorded on the same outpatient data sheet as described in item B above.

D. Transfusion: Number of transfusions will be recorded and compared between both groups. Transfusion criteria will not deviate from our normal post-operative care protocol.

E. Wound Complications: the incidence of wound infection and wound drainage will be assessed and recorded. Compressive dressings will be changed daily until wound is dry. If wound is draining at hospital discharge, the patient will be provided with home dressing supplies and instructed on how to perform daily dressing changes. The patient will take a daily photo of the wound and removed dressing daily and email it to CJR until the wound is dry. This is standard protocol for our patients currently.

F. Thromboembolic Disease: Screening will be based on clinical assessment of the participating medical team members, which is standard protocol with all of our patients. The incidence of thromboembolic events will be recorded. All patients in the study will use aspirin 81 mg twice daily for DVT prophylaxis.

G. Muscle Strength: quadriceps strength will be assessed on POD #1 and 2 by research staff (in the hospital) and repeated at 2 and 6 weeks postoperatively at their standard of care follow-ups in the office by research staff. The strength testing will be calculated using a handheld dynamometer which is standard testing for strength in many post-operative patients currently.

H. Functional Performance Assessment: Functional tests will be performed at their preoperative appointment and once again at their 2 and 6 weeks postoperatively and will include the timed up and go (TUG) and the 30 second sit-to-stand tests. The tests will be performed in the office by research staff. These are standard tests that are often performed in physical therapy clinics to assess patient progress.

I. Length of the Hospitalization & Readmission Incidence will be recorded for both groups.

J. Postoperative Pain Assessment: Pain will be assessed using a pain VAS scale daily while hospitalized, then three times per day for 4 weeks postoperatively. Patients will be given a log to record these measurements outside of the hospital setting.

K. Adverse Events: episodes such as symptomatic hypotension (light-headedness, syncope), emesis, the need the IV fluid boluses, and other hospital and post-discharge events will be recorded.

L. Blood Pressure: this will be recorded in the Preoperative Care Unit, PACU, upon arrival to the nursing unit, and every 8 hours thereafter while hospitalized. This is standard practice for all of our patients currently.

M. PONV (Post-operative Nausea and Vomiting) - PONV will be assessed throughout their hospital stay; vital signs are checked per hospital nursing protocol, patients will be asked about Nausea: None, Mild, Moderate or Severe.

N. Patient Reported Outcome – We will be collecting the Knee Society Score(KSS) Knee injury and Osteoarthritis Outcome Score (KOOS) and the VR-12 from the patients pre-operatively as well as at their 2 week and 6 week follow up appointments. These are validated patient reported outcome measures that are already collected as standard of care at Colorado Joint Replacement.

O. Pressors – We will be collection the total amount of any pressor drugs (e.g. Ephedrine and Phenylephrine) given intra-operatively and in PACU in both groups.

P. Oral Fluid Intake Log – The patients that are in the Oral group will have an additional page to keep track of their fluid intake prior to surgery.

Q. Bioimpedance machine - This will be used to track patients body composition before and after surgery. Research staff in the office will collect this information at the patient's pre-op visit, POD#1 and 2 as well as their 2 week and 6 week visit.

R. Body Temp – The patient's body temp will be recorded pre-operatively as well as in the recovery room.

S. Time from their last clear fluid drink to the start of anesthesia, this start up time will be recorded for both groups.

T. Patient perception/satisfaction with their fluid protocol.

Patient Withdrawal: subjects may withdraw from the study for any reason at any time. Should a subject decide to withdraw from the study, all data collected up to that point will be deleted and not used for statistical analysis. Withdrawal from the study will not affect the patient's treatment after their total knee arthroplasty.

3. Scientific Background of the Study – As stated in the “purpose” section –

Evidence-based guidelines on optimal perioperative fluid management have not been established in patients undergoing orthopaedic surgery. Recent randomized trials in major abdominal surgery suggest that large amounts of fluid may increase morbidity and hospital stay. This study will investigate the effects of two regimens of intraoperative fluid management (“traditional” vs. “oral”) with physiologic and patient function as primary outcome measures after surgery.

4. Specific Aims of the Study – This study will investigate the effects of two regimens of intraoperative fluid management (“traditional” vs. “oral”) with physiologic and patient function as primary outcome measures after surgery.

5. Description of risks and measures to minimize risks.

- All patients, regardless of their volume protocol (traditional vs. oral), will follow a traditional post-operative course which includes daily labs and monitoring physiologic status from both the orthopaedic and general medicine team.
- All patients will have traditional post-operative follow-up care which will not be varied.

Surgical Risks:

There are risks and complications that are associated with all artificial knee surgeries. These have all been discussed with you by your surgeon's team prior to surgery. You are at no increased risk of known complications in this study.

Testing Session Risks:

Though the procedures that you will be exposed to are safe, discomforts you may experience while in this study include:

- Commonly - muscle soreness after muscle strength testing for approximately 2 days after testing. This soreness is similar to the muscle soreness that you may feel if you lift weights or vigorously exercise after a long time off
- Less commonly – muscle strains or tears

The study may also include risks that are unknown at this time.

The investigators have a data safety monitoring plan (DSMP) that includes the Principal Investigator monitoring confidentiality, protection of subject privacy, database protection, confidentiality during adverse event reporting, adverse event information including definitions of adverse events, classification of adverse event severity, adverse event attribution scale, expected risks, adverse event reporting and follow-up, serious adverse event reporting, data quality and management, participant accrual and compliance, measurement and reporting of participant adherence to protocol, designation of an independent physician, informed consent process, and reporting change in study status. In addition, to monitor the safety of the subjects enrolled every quarter an independent physician will review the studies adverse events as well as inclusion/exclusion to ensure there is no increased risk to subjects who are taking part in the study. Study staff will ensure that the IRB is informed in a timely manner of any recommendations, decisions, findings, actions, or steps mandated by the DSMP.

6. Benefits to subjects and/or society.

- Other studies (non-orthopaedic) have shown benefits with wound healing and a potential decrease in adverse events after abdominal surgical procedures. It is unknown if there will be a difference between the two protocols in our study. The potential benefits to the oral group include decreased wound complications, improved functional outcomes and the potential for a decrease in healthcare expenditure per surgery.

Patient Selection Criteria

INCLUSION

- Patients between the ages of 18-75 years old undergoing a primary total knee arthroplasty for a diagnosis of degenerative osteoarthritis who do not meet the exclusion criteria listed below.

EXCLUSION – patients will be screened for the following exclusion criteria at their routine preoperative appointment with the orthopaedic and internal medicine teams.

- Volume-dependent cardiac conditions:
- Aortic stenosis
- Pulmonary valve stenosis
- Subaortic stenosis
- Severe Aortic Insufficiency
- Chronic systolic heart failure
- Eisenmeinger Syndrome
- Severe pulmonary HTN
- Chronic or paroxysmal dysrhythmias
- Pre-operative electrolyte abnormalities
- Abnormalities of the HPA (hypothalamic-pituitary axis)
- Stage 3 Chronic Kidney Disease (or worse)
- Patients taking angiotensin receptor blockers (ARB)
- Patients with uncontrolled diabetes mellitus (patient with A1C of 7+ or on insulin)
- Patients whose BMI is > 38 or < 19

- Current use of long acting narcotic medication or 3 or more months of daily short acting narcotic medication
- Patients at risk for electrolyte abnormalities, dehydration or intra-operative hypotension. (patients taking angiotensin receptor blockers, ACE inhibitors (48 hours prior to surgery) and Diuretics)
- Patients with severe, untreated or uncontrolled GERD.
- Patients that cannot receive spinal anesthesia (e.g. patient with back fusions)
- Pre-Operative Anemia (pre op HCT <30%)

7. Treatment/Intervention Schedules or in the case of observational studies:

- As per section #2

8. Data Collection Procedures

- Preoperative history and physical will be performed as usual by the surgeon and/or their physician assistant. The patient will also be evaluated preoperatively (per standard procedure) by the general medicine team as well.
- Please refer to section 2 and 8 for the outcome measures, how they will be collected and the time intervals designated.
- Data will be stored on a password protected Microsoft Excel spreadsheet on a Centura approved secure computer.
- All data collected will be de-identified.

9. Methods of Evaluation

Based on my reading of the fluid management protocol, the study evaluates the hypothesis that the euvoolemia regimen leads to better outcomes than the traditional regimen. The former corresponds to the treatment group and the latter to the control group for the analysis, and assuming that the two groups demonstrate similarities in terms of potential pre-treatment confounding variables, such as measures obtained from preoperative history and physical, a comparison of post-treatment outcomes seems appropriate (e.g., t-tests). Even under random assignment to treatment, checks can be performed to ensure effective equivalence of confounders across treatment and control groups, an essential step in the case of small samples. If the results of such checks reveal potential confounding, including control variables in the analysis may be appropriate (e.g., in a linear regression) or a matching design to generate treatment-control pairs can be used.

While I do not have any substantive training in this field, it seems that some of the outcomes listed in the Procedures: Primary Outcomes section of the protocol may be mediated by others. For example, the association between receiving the treatment and readmission or length of hospitalization may be mediated by some of the other outcomes listed. Are there any known or suspected mediators at this point, either from the list of outcomes or beyond?

Concerning statistical power, in the figure below I calculate power (y-axis) for a range of hypothesised values of estimated effect sizes (colored lines), sample sizes per treatment and control group (x-axis), and arbitrarily chosen levels of significance (α) across the panels. Regarding α , I start with 0.05 and then make an adjustment based on an arbitrary number of hypotheses to be evaluated (eight, in this demonstration). The solid horizontal line at 0.8 represents the commonly accepted power value. As an example from Figure 1(b), for a medium-high effect size of 0.6 (green line) and evaluating eight hypotheses, in order to achieve power of 0.8 would require approximately 65 participants in each of the treatment and control groups.

[figure not shown]

Figure 1: Power calculations for hypothetical effect sizes and sample sizes (per group) at given values of α . The left panel uses $\alpha = 0.05$ and the right panel employs a Bonferroni correction for multiple hypotheses. In this case, evaluating eight hypotheses with a desired α of 0.05 yields an adjusted α of 0.00625.

10. Trial Design

- Please refer to the above sections regarding the discussion of the research study
- Patients will be identified based on the inclusion and exclusion criteria stated above. The patients will then be randomized into the “traditional” vs. oral arms of the study. Outside of the amount of preoperative, intraoperative and postoperative fluids given to the patients, there is no difference in the treatment or outcome measures between the 2 groups.

11. Statistical calculations- please refer to section 10, methods of evaluation

12. Confidentiality of the data.

- Data will be collected on a password protected excel spreadsheet that will be stored on a Centura password protected computer.
- All data collected will be de-identified.

Data sharing.

With whom will *identifiable* (contains any of the 18 identifiers) data be shared outside the immediate research team? For all that apply, explain confidentiality measures. Include data use agreements, if any.

Data will be shared with:		Name/Description/s
	No one	
	Coordinating Center	
	Statisticians	
x	Other researchers	[name]; [name]; [name]; [name], , [name], [name] (research coordinator), [name] (research data entry clerk), [name] (clinical research associate).
	Registries	
	Sponsor/s	
	External labs for additional testing	
	Journals	
	Publicly available dataset	
	Other	

Data security for storage and transmission. Include all that apply.

For electronic data stored on a desk top computer:

 Secure network	 Password access	 Data encryption	 Password protected file(s)
 Other comparable safeguard (describe):		Data will be de-identified	

For portable computing devices/external storage devices (e.g. laptop computer, PDA, CDs, memory sticks):

 Power-on password	 Data encryption
 Automatic log-off	 Password protected file(s)
 Other comparable safeguard (describe): Data will be de-identified	

For hardcopy data (including human biological specimens, CDs, tapes, etc.):

 Data de-identified by research team (stripped of the 18 identifiers)	 Locked suite or office

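### Arms are assigned by a free pick from sealed envelopes with no stated order, numbering, custody or log, so the arm could be changed after consent without a record; the 130 envelopes also fall short of the 150 planned patients.

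*Combined protocol and SAP*

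**What the plan says.** Allocation is described in one place, section 2 (Procedures): "The protocol for each group will be placed in sealed envelopes, 65 for each group, and picked randomly for each patient". The sentence before it says only that patients are randomised to the two groups. Section 10 (Trial Design) repeats that and adds no method. Section 14 lists an attachment titled Random Envelope selection, but its content is not in the text supplied.

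Four other statements bear on the point:

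- **Recruitment.** Research staff recruit in clinic, and consent is listed before randomisation: "The patients will be approached regarding the study (in clinic by research staff) and if the patient is agreeable, informed consent will be obtained".
- **Numbers.** The last bullet of the general procedures in section 2 raises the target: "We will increase our number of enrollment to 75 in each group to account for patients that drop out and withdrawals from the study".
- **Eligibility.** Section 10 puts eligibility before randomisation: "Patients will be identified based on the inclusion and exclusion criteria stated above". The exclusion list says "patients will be screened for the following exclusion criteria at their routine preoperative appointment with the orthopaedic and internal medicine teams", and section 2 lists the preoperative visits after randomisation.
- **Outcome measurement.** Under Primary Outcomes in section 2, research staff take the in-hospital range-of-motion and girth measurements (items B and C), quadriceps strength (item G) and the functional tests (item H). No blinding is described anywhere.

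**The concern.** Concealment depends on the next patient's arm being fixed before that patient is known, and on any departure from the fixed order leaving a mark. A free pick from a pool gives neither. No particular envelope belongs to a particular patient until someone chooses it, so choosing again breaks no visible rule. Sealing is the only safeguard stated, and it does not prevent a second pick.

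The risk matters more here because the fluid regimens are evident to those giving and receiving them, and because staff who recruit also measure outcomes. If some patients were moved between arms according to how well they were expected to do, outcomes related to that prognosis would differ between arms with no treatment effect.

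**Working it through.** **1. Safeguards, checked against the text of section 2**

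| Safeguard | Stated? |
|---|---|
| Sealed envelope | Yes |
| Order generated in advance | No; the pick itself is the randomisation |
| Sequential numbering | Not stated |
| Opaque envelopes, identical contents | Not stated; the content is the arm's protocol |
| Preparer or holder independent of recruitment | Not stated |
| Patient identity written on the envelope before opening | Not stated |
| Allocation log | Not stated |

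Even if the envelopes carry numbers, picking them at random means the numbers do not fix the order.

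**2. Envelope count**

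- Envelopes: 65 + 65 = 130.
- Planned enrolment: 75 + 75 = 150.
- Shortfall: 150 − 130 = 20 patients, or 20/150 = 13.3%.

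The text does not say how these 20 are allocated, or whether envelopes from withdrawn patients return to the pool.

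**3. The plan's own figure**

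The 65 per group comes from section 9: effect size 0.6, power 0.80, α = 0.05/8 = 0.00625. A one-sided t-test needs 64 per group, which matches about 65. A two-sided test needs 72 (normal) or 73 (t). The sidedness is not stated. This does not affect the allocation point; 65 is used below only to set the standard error.

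**4. Can the next arm be guessed from a tally?**

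In a simulation of 40,000 sequences drawn without replacement from a 65/65 pool, the best guess was right 55% of the time overall, 52% over the first 65 draws and 65% over the last 20. Prediction is weak until late, so the main exposure is the unrecorded re-pick.

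**5. Size if allocations were steered (illustration)**

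Neither of these inputs is in the documents; both are assumptions:

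- *f*: the share of allocations decided by prognosis, with better-than-median patients sent to one arm and the rest to the other.
- *r*: the correlation of prognosis with the outcome.

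With standard normal prognosis, the two halves differ in mean by 2√(2/π) = 1.60 SD. Hence:

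- Bias = r × f × 1.60 SD.
- SE = √(2/65) = 0.175 SD.
- Error rate = P(|N(bias/SE, 1)| > 1.96) for a two-sided 5% test.

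| r | f | Bias (SD) | Bias/SE | Error rate |
|---|---|---|---|---|
| 0.3 | 5% | 0.02 | 0.14 | 5.2% |
| 0.5 | 5% | 0.04 | 0.23 | 5.6% |
| 0.5 | 10% | 0.08 | 0.45 | 7.4% |
| 0.5 | 20% | 0.16 | 0.91 | 14.9% |
| 0.7 | 20% | 0.22 | 1.27 | 24.7% |

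At the Bonferroni level of 0.00625 used in section 9 (two-sided), r = 0.5 gives 1.2% for f = 10% and 3.4% for f = 20%. These are 0.012/0.00625 = 1.9 and 0.034/0.00625 = 5.4 times nominal.

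**The case against.** The strongest reply is that silence is not absence. The envelopes are sealed, and a dedicated attachment on envelope selection exists that may set out numbering, custody and a log. That stands as far as it goes: a reader might infer a heap of unnumbered envelopes, but the documents say neither. What the attachment cannot change is that section 2 describes a free pick, which an ordered procedure would contradict.

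Four further inferences are tempting, and the documents do not support them:

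- **Steered recruitment.** This needs knowledge of the next arm before consent. Consent is listed first, a free draw has no preset next arm, and a tally predicts only 55% of draws. What remains is changing the arm after consent.
- **Recognising the arm by thickness or weight.** The oral group does have an extra sheet: "The patients that are in the Oral group will have an additional page to keep track of their fluid intake prior to surgery". But nothing puts it in the envelope, and either protocol might fit on one page. It is a possibility only.
- **Bias that no analysis could detect or repair.** Section 9 provides for baseline checks and for regression or matching if they show imbalance. Preoperative motion, girth, function and patient-reported scores are collected. Steering on measured factors could be partly found and adjusted for; steering on unmeasured judgement could not.
- **Everyone knows the arm, and every outcome is biased.** Outpatient therapists measure motion and girth at weeks 1 to 4, and nothing says they are told the arm. Only outcomes correlated with prognosis would be biased.

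It is also fair to say that the illustration rests wholly on assumed values, supposes perfect sorting of steered patients and no adjustment, and is close to nominal at f = 5%.

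**Conclusion.** The point holds as a weakness in the allocation rule. Section 2 prescribes a method that fixes no order, and the visible text gives no means of noticing an arm changed after consent. The shortfall of 20 envelopes against planned enrolment is shown directly by the plan's own numbers and needs no assumption.

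The size of any bias is unknown. With r = 0.5, steering 10% to 20% of allocations gives 0.08 to 0.16 SD and a two-sided 5% error rate of 7.4% to 14.9%. Over r = 0.3 to 0.7 and f = 5% to 20%, the rate runs from 5.2% to 24.7%. A reader might take these figures as a sign that steering is expected or has happened; nothing in the documents suggests either. The case for change is that a better method is available at very little cost. Confidence is medium, because the attachment has not been seen.

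**What to change.** Replace the envelope sentence in section 2 with an ordered, recorded procedure:

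1. Someone outside recruitment generates the 1:1 order by computer before the first patient, sized to the planned 75 + 75, and holds the list away from recruiting staff.
2. One identical card per patient goes into an opaque, sequentially numbered envelope. The arm's protocol pages are handed out only after opening.
3. Envelopes are opened strictly in number order, after consent and confirmed eligibility. Study number, date and initials are written on the sealed envelope first. Section 2 and the exclusion list should be reconciled with section 10, so that screening clearly comes before allocation.
4. Opened envelopes and an allocation log are kept.

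The cost is a few hours of preparation, one log, and the need to keep the list secure. The arms, the ratio and the enrolment target do not change. If the attachment already specifies these steps, it is enough to bring the section 2 wording and the envelope count into line with it.

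### Section 10 says the arms differ only in fluid amounts, but Section 2 sets a different food fast in each arm, so outcome differences cannot be credited to fluid alone

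*Combined protocol and SAP*

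**What the plan says.** Section 2 gives each arm its own fasting instruction. The Traditional Fluid Protocol uses a fixed clock time for food and clear liquids together: "NPO Clears and Food after midnight". The Oral Fluid Protocol counts back from surgery: "NPO Food/Milk: none beginning 8 hours prior to procedure time". It adds a clear drink closer to surgery: "Patients are asked to drink 10 ounces of clear liquid 4 hours prior to their scheduled procedure time".

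Section 10 (Trial Design) summarises the contrast as follows: "Outside of the amount of preoperative, intraoperative and postoperative fluids given to the patients, there is no difference in the treatment or outcome measures".

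Section 4 (Specific Aims), like Sections 1 and 3, gives the aim as studying "the effects of two regimens of intraoperative fluid management". Section 1 describes the oral group more broadly, as "patients who are given a specific protocol preoperatively to optimize hydration, followed by limited fluids intraoperatively based on physiologic parameters".

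The only preoperative fasting interval listed for collection is item S: "Time from their last clear fluid drink to the start of anesthesia, this start up time will be recorded for both groups". Among the items under Primary Outcomes are body weight with a preoperative reading in the holding area (A), adverse events including emesis and light-headedness (K), nausea and vomiting (M) and satisfaction with the assigned protocol (T).

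**The concern.** The food rule is a second assigned difference between the arms, and Section 10 says there is none. It looks unplanned. The spinal drug and dose range, ondansetron, nerve block and postoperative diet are all matched across the arms. Section 1 gives hydration as the purpose of the preoperative protocol, and no reason for a different food rule appears.

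What is at stake is what the trial may claim. If the oral arm has less nausea or emesis, a report that follows Section 10 and the Specific Aims would credit fluid, and intraoperative fluid in particular, although part of the difference could come from food timing. Randomisation does not separate the two, because both belong to the assigned regimen. Weight is exposed through its baseline. The reference reading is taken after the two different fasts, and the extra 3-week weighing is triggered by a change of more than 2% from the preoperative value. The visible plan lists no last-meal time, so the food component could not be examined afterwards.

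**Working it through.** The plan gives no figure for this contrast, so there is none to reproduce. The check sets the passages side by side and works out the assigned gap.

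**Step 1: consistency.** Section 10 allows one kind of difference, the amount of fluid before, during and after surgery. Section 2 ends solid food at midnight in one arm and 8 hours before the procedure in the other. A time limit on food is not an amount of fluid, so both statements cannot be true.

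**Step 2: size of the food gap.** Inputs: the midnight cut-off (Traditional Fluid Protocol), the 8-hour cut-off (Oral Fluid Protocol) and the start hour *h*. The documents do not give *h*; 07:00 to 15:00 is assumed.

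- Minimum food fast, traditional arm = *h* − 0 = *h* hours
- Minimum food fast, oral arm = 8 hours
- Gap, traditional minus oral = *h* − 8

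For comparison, the gap since the last permitted or requested clear drink (midnight versus 4 hours before) is *h* − 4. That gap belongs to the intended fluid contrast.

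| Assumed start | Food fast, traditional (h) | Food fast, oral (h) | Food gap (h) | Clear-drink gap (h) |
|---|---|---|---|---|
| 07:00 | 7 | 8 | −1 | +3 |
| 08:00 | 8 | 8 | 0 | +4 |
| 10:00 | 10 | 8 | +2 | +6 |
| 12:00 | 12 | 8 | +4 | +8 |
| 15:00 | 15 | 8 | +7 | +11 |

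The food gap is nil at 08:00, reverses before then and grows through the day.

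**Step 3: permitted cut-offs are not meals.** The oral-arm cut-off falls at *h* − 8 on the clock: 02:00 for a 10:00 start and 04:00 for a noon start. If patients sleep overnight, few would eat in those windows. A meal at 06:00 is permitted only from a start of 6 + 8 = 14:00. The gap in actual eating may therefore be smaller than the table shows.

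**Step 4: the aim against the assigned contrast.** Taking 1 oz as 29.57 ml:

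- Oral arm, each of the 3 days before surgery: 3 × 20 × 29.57 = 1,774 ml; over 3 days, 5.32 L as a minimum
- Oral arm, 4 hours before surgery: 10 × 29.57 = 296 ml, about 0.30 L
- Oral arm, IV from the holding area until stopped in the PACU: at most 0.5 L
- Oral arm, 3 days after surgery: again at least 5.32 L by mouth
- Traditional arm: 4 L of crystalloid, of which 2 L during surgery and 0.5 + 1.5 = 2 L afterwards

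Much of the assigned difference therefore lies outside the operating room, and the word intraoperative in the aim is narrower than what is randomised, quite apart from food.

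**The case against.** The strongest reply is that food timing sits inside each assigned protocol, so the randomised comparison is not confounded. Section 1 already speaks of regimens and describes a preoperative component, and comparing whole packages is a legitimate design. On this view, what remains is an incomplete summary sentence and one loose adjective. The point about validity stands in full: any difference between arms can be attributed to the regimen. What it does not rescue is Section 10, which excludes any difference other than fluid and would license a narrower claim than the design supports.

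A reader might go further and infer that differences in nausea, emesis, weight and satisfaction cannot be credited to fluid at all. The documents do not support that. The planned fluid contrast is large, 4 L of crystalloid against at most 500 ml IV plus oral loading, and it may well be the main influence on weight. Nothing in the documents says how much a few hours of food fasting changes any outcome, so a large food effect is as unproven as a negligible one. Nausea, emesis and the holding-area weight are the plausible examples. Later weights are touched only if analysed as change from that baseline. Satisfaction is a weak example, because item T asks about the assigned protocol as a whole.

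Two other objections also hold. The size and direction of the gap depend on start times that the documents do not give. And Section 14 lists a Patient Data Log that is not shown, so the absence of a last-meal time can be asserted only for the visible plan.

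**Conclusion.** The contradiction between Section 10 and the two food rules in Section 2 is certain and rests on no assumption. The consequence is limited. The comparison of regimens remains valid, while attribution to fluid alone is not supported, and attribution to intraoperative fluid alone is supported even less.

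The gap in permitted food fast is the start hour minus 8. It runs from −1 to +7 hours over assumed starts of 07:00 to 15:00, and actual meals may differ less. The documents do not allow the effect on any outcome to be estimated, in size or in direction. The correction is worth making because it changes what the trial may conclude and costs very little.

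**What to change.** 1. Reconcile the two fasting instructions in Section 2 with the statement in Section 10. Which food rule applies, and whether it is common to both arms, is for the investigators and anesthesia to decide; this review takes no position.
2. If the difference stays, correct Section 10 and the Specific Aims, with the matching sentences in Sections 1 and 3, to say that the trial compares two whole perioperative regimens, including food fasting. Drop the attribution to intraoperative fluid.
3. In either case, record the time of last solid food in both arms beside item S, so that the actual food fast can be described by arm.

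The cost is one added form field and a few lines of text. The downside is a less specific claim if the regimens keep different food rules.
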